#### 7.4.5 Neutropenia

Drug effects on neutrophils will be assessed by the laboratory analyses described in [section 7.3.2](#), additionally decreased neutrophil counts (occurrence of neutropenia) per CTC grades as shown in [table 7-8](#) will be reported and baseline neutrophil / white blood cell counts will be taken into account in this analysis. Shifts versus baseline will also be shown per CTC grade.

Whether baseline neutropenia or early drops in neutrophil counts (or neutropenia) are indicative of infections (defined using adjudicated events of infection, investigator reported infections, and AEs of special interest) will be explored in two separate Cox regression models; one including treatment, baseline neutropenia and the interaction term as covariates, and the second model including treatment, early drops in neutrophil counts (or neutropenia) and the interaction term as a covariate. There are two definitions for the early drop in neutrophil counts (or neutropenia) subgroup, one using an ordinal variable and one using percentage change from baseline, and these are both computed at visits 3 and 4, see Table 2.3-3. There will therefore be four models for this endpoint and these will be displayed in the same table.

[figure not shown]

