5.3 Treatment assignment

At pivotal phase Visit 2, all eligible patients will be randomized via Interactive Voice Response System /Web System (IVRS/IWRS) to one of the treatment arms. The investigator or his/her delegate will contact the IVRS/IWRS after confirming that the patient fulfills all the inclusion/exclusion criteria. The IVRS/IWRS will assign a randomization number to the patient, which will be used to link the patient to a treatment arm and will specify a unique medication number for the first package of study drug to be dispensed to the patient. The randomization number will not be communicated to the caller.

In trial part 1 prior to the implementation of protocol amendment 6 at each site, there was a single randomization plan. In trial part 2 (following protocol amendment 6) this trial has two randomization plans A and B. The IVRS/IWRS randomly assigns patients to plan (A and B) and treatment. Randomization plan A includes placebo, 150 mg and 300 mg canakinumab arms and therefore, is fully blinded. Patients assigned to randomization plan A will receive two 1 mL injections at each trial visit except at visit 3 (1.5 months). Randomization plan B includes placebo, 50 mg and 150 mg canakinumab arms, and is also fully blinded. Patients assigned to randomization plan B will receive one 1 mL and one 0.5 mL injections at each pivotal phase visit except at visit 3 (1.5 months). The randomization numbers will be generated using the following procedure to ensure that treatment assignment is unbiased and concealed from patients and investigator staff. A patient randomization list will be produced by the IVRS/IWRS provider using a validated system that automates the random assignment of patient numbers to randomization numbers. These randomization numbers are linked to the different treatment arms, which in turn are linked to medication numbers. A separate medication list will be produced by or under the responsibility of Novartis Drug Supply Management using a validated system that automates the random assignment of medication numbers to study drug packs containing each of the study treatment.

In the extension phase all participants except for those with prediabetes will remain on their randomization number assigned at randomization in the pivotal phase until they switch to an

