9.4.4 Supportive analyses

[figure not shown]
The components of the composite primary efficacy endpoint (CV death, fatal or non-fatal MI, fatal or stroke) will also be analyzed individually in order to evaluate their contributions to the overall treatment effect.

The primary endpoint will also be analyzed on the PPS. Additionally in an on-treatment analysis on the FAS patients will be considered censored at the latest one quarter year + 28 days (119 days) after the last study injection. Besides adjudicated endpoints investigator reported outcomes will also be analyzed.

The three pooled canakinumab doses will be compared to placebo on the primary composite endpoint and its components, because in case of similar efficacy on all three doses this would be the most powerful test of the scientific hypothesis addressed by this trial. Additionally, when all three doses have similar efficacy such a pooled analysis approach may be able to provide the most precise information on the effects in subgroups. Methods to evaluate dose response in terms of cardiovascular events will also be pre-specified in the detailed statistical analysis plan.

Furthermore, pre-specified subgroup analyses will include age, sex, race, ethnicity, BMI, region, glycemic status, smoking status, baseline hsCRP level, LDL-C levels, SBP/DBP levels, statin, aspirin, gout and renal failure. Possible interactions between treatment and baseline variables will be evaluated with appropriate methods. Results will be presented graphically as forest plots. The objective of the subgroup analyses is to show the consistency of treatment effects across a wide variety of patient groups. Additional subgroup analyses will be considered and pre-specified prior to unblinding of trial database for final analysis. Additionally, the post-baseline subgroups of response in hsCRP response and target hsCRP levels achieved will be explored.

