Early drops in platelet counts (or thrombocytopenia) defined by % change from baseline	< 20% and ≥ 20% drop from baseline to visit 3. Repeat at visit 4
Early drops in neutrophils (or neutropenia)	<0.5, ≥0.5 - <1.0, ≥1.0 - <1.5, ≥1.5 - <LLN at visit 3. Repeat at visit 4
Early drops in neutrophils (or neutropenia) defined by % change from baseline	< 20% and ≥ 20% drop from baseline to visit 3. Repeat at visit 4
baseline neutropenia	CTC ≥3 (yes/no)

To support regional submission activities and health authority interactions, at a minimum the subgroups shown in [table 2.3-4](#) are needed.

**Table 2.3-4 Regional/country subgroups to support regional/local submissions, for which selected tables have to be repeated**

Preliminary* list of variable(s) / analyses to be repeated	Regional/country subgroup
On FAS Disposition/Demography/Patient and disease characteristics Incidence of primary endpoint Incidence of key secondary endpoints Incidence of secondary endpoints (includes death) Analyses of other selected efficacy variables (e.g. hsCRP) Medical environment (e.g. prior/concomitant medications including statin dose, revascularization/stenting/etc. for index MI)	1. Japan 2. Japan and Korea 3. Mainland China 4. Mainland China + Taiwan 5. Asian patients: Japan, China, Taiwan, and Korea 6. India 7. Russia
On SAF Adverse events by system organ class and preferred term Serious adverse events by system organ class and preferred term Deaths Standardized MedDRA queries	

[figure not shown]
Preliminary* list of variable(s) / analyses to be repeated	Regional/country subgroup
Adverse events of special interest	

\* subject to changes dependent on local requirements

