**Table 2-4 Time windows for endpoints based on HbA1c, FPG, standard hematology, biochemistry or fasting lipid profile**

Time window	Start of time window (study days)	End of time window (study days)
Week 2 visit	1, but only after the laboratory assessment of the baseline visit	28
Month 1.5 visit	29	68
Month 3 visit	69	137
Month 6 visit	138	228
Month 9 visit	229	320
Month 12 visit	321	457
Month X visit (where X≥18 is a multiple of 6)	$\text{Rounded} [ ( 365.25 / 12 ) * ( X - 3 ) ] + 1$	$\text{Rounded} [ ( 365.25 / 12 ) * ( X + 3 ) ]$

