**Table 7-5 Higher Risk Subgroups**

Elderly	>=65 years (yes/no)
Diabetics	based on diabetics definition in Table 2.3-1 (yes/no)
Low baseline neutrophils	CTC >=3 at baseline (yes/no)
Current smokers	Current smokers (yes/no)
Obese patients	BMI >=35kg/m  at baseline (yes/no)
Regions	The same as above in Table 2.3-1
Asthma patients	PT="Asthma" in MH (yes/no)
COPD patients	PT="COPD" in MH (yes/no)

It will be explored whether any potential risk of infections changes based on whether patients have reported a vaccination within 3 months from/including baseline (yes/no), by modelling the time to first infection including treatment, subgroup (vaccination within 3 months, yes/no), and treatment\*subgroup. This analysis will also be done for the 6 month time frame (yes/no - live vaccination within 6 months from/including baseline).It should be noted that live vaccinations within 3 months were not permitted in this study.

Separate summaries of infections and tuberculosis related adverse events (defined by HLTs "Tuberculous infections" and "Mycobacteria identification and serology") will be produced for the patients who had tuberculosis, latent or suspected tuberculosis at the start of the study and received randomized study medication. A patients' listing will be provided.

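### SAP 7.4.5 relates infections counted from randomization to a neutrophil drop first measured at month 1.5 or month 3, with no landmark or time-dependent coding

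*SAP*

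**What the plan says.** SAP 7.4.5 plans two Cox models for infection. One uses baseline neutropenia, which is a proper baseline covariate. The other uses a post-randomization measurement: "the second model including treatment, early drops in neutrophil counts (or neutropenia) and the interaction term as a covariate". The drop has an ordinal definition and a percentage-change definition, and "these are both computed at visits 3 and 4, see Table 2.3-3". Table 2.3-3 gives the percentage version as "< 20% and ≥ 20% drop from baseline to visit 3. Repeat at visit 4".

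Visit 3 falls at month 1.5; Protocol 5.3 describes injections at each visit "except at visit 3 (1.5 months"). Visit 4 is month 3 in Protocol Table 6-1. SAP Table 2-4 sets the haematology windows in study days: "Month 1.5 visit 29 68" and "Month 3 visit 69 137".

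The events start earlier. SAP 7.3.1 includes adverse events with onset after randomization, and the infection time periods in SAP 7.4.1 begin at randomization. The default safety Cox model in SAP 7.2 has fixed covariates and no delayed entry. Time-dependent period variables appear in SAP 7.4.1, but only to see whether treatment differences change over time.

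SAP 7.4.1 also models time to first infection by "whether patients have reported a vaccination within 3 months from/including baseline (yes/no"), and by live vaccination over 6 months. It does not say whether either window runs before or after baseline.

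**The concern.** Whether an early drop foretells infection is a forward-looking question. With the clock at randomization and the drop as a fixed covariate, an infection on day 10 is related to a blood count taken around day 91.

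Two things follow. Infections that happened before the drop was known carry no information on what the drop predicts, so they dilute a real association. If infection itself raises or lowers the count, they can also create a false association in either direction, including in the interaction with treatment. In addition, a patient with no Visit 3 or Visit 4 sample has no covariate value, and 7.4.5 gives no rule for such patients.

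Infections and neutropenia are both listed safety topics (SAP Table 7-4). SAP section 7 says this is intended to be the only pivotal trial in the submission, so a misleading link between the two could affect how the risk is described.

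**Working it through.** **1. The plan's own figures.** Two definitions × two visits = 4 models, as SAP 7.4.5 states. With one month = 365.25/12 = 30.44 days, the midpoint between months 1.5 and 3 is 2.25 × 30.44 = 68.5 days, and between months 3 and 6 it is 4.5 × 30.44 = 137.0 days. Table 2-4 has 68 and 137. The visit timing is therefore as described.

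**2. Share of first infections before the sample.** The documents give no infection rate. I assume a constant rate r of 3 to 40 per 100 person-years and follow-up F of 3 to 4 years. For a sample on day d:

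share = (1 − exp(−r·d/365.25)) / (1 − exp(−r·F))

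Example with r = 0.10 and F = 4: the denominator is 1 − exp(−0.4) = 0.330. At day 91 the numerator is 1 − exp(−0.0249) = 0.0246, a share of 7.5%. At day 46 it is 0.0125, a share of 3.8%.

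| Sample | Lowest (r = 0.03, F = 4) | Highest (r = 0.40, F = 3) |
|---|---|---|
| Visit 3, day 46 | 3.3% | 7.0% |
| Visit 4, day 91 | 6.6% | 13.6% |
| Month 1.5 window, day 29 to day 68 | 2.1% (day 29) | 10.3% (day 68) |
| Month 3 window, day 69 to day 137 | 5.0% (day 69) | 19.9% (day 137) |

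**3. Effect on the hazard ratio.** Simulated Cox model with one binary covariate: 10,000 patients, 4 years, 60 replicates, rates of 5, 10 and 20 per 100 person-years, and 20% with a recorded drop. All are assumptions, as are the effects of infection on the count. Ranges run over the three rates.

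| Scenario | Visit 3, clock from randomization | Visit 4, clock from randomization | Landmark at the visit |
|---|---|---|---|
| True HR 1; infection does not alter the count | 0.99-1.01 | 0.99-1.00 | 0.99-1.00 |
| True HR 1; earlier infection doubles the chance of a drop (20% to 40%) | 1.03-1.05 | 1.09-1.12 | 0.98-1.01 |
| True HR 1; earlier infection halves it (20% to 10%) | 0.97-0.99 | about 0.95 | 1.00-1.01 |
| True HR 1.5; infection does not alter the count | 1.47-1.48 | 1.46-1.47 | 1.49-1.51 |

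**4. Interaction.** The simulation in step 3 has no treatment term. A smaller one did (10,000 patients, 2:1 active to placebo, rates of 10 and 30 per 100 person-years, 12 replicates). If earlier infection doubles the chance of a drop on active drug only, and nothing truly differs, the interaction ratio is 1.09-1.13 from randomization and 0.98-1.04 with a landmark. It is noisy, and shows only that a false interaction of this kind is possible.

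**The case against.** The best defence is that the SAP never says the drop is treated as known at randomization. That is inferred from silence about the clock. SAP section 1 says a more detailed plan with data set specifications will follow. The models are exploratory, SAP 7.1 makes no multiplicity adjustment for safety, and the main infection results are comparisons between arms and baseline subgroups. The distortion needs an assumed effect of infection on the count; without one, there is no bias at a true hazard ratio of 1. All of this stands and limits the weight of the point. It does not remove it: the readable text counts infections from randomization and states no safeguard, so a programmer following it would build the model described.

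A reader might infer that the vaccination model has the same fault. The documents do not establish that. The phrase "whether patients have reported a vaccination within 3 months from/including baseline (yes/no") gives no direction. The adjoining remark, that live vaccination within 3 months was not permitted, matches exclusion 8 in Protocol 4.2, which looks back from randomization. Protocol 5.5.7 prohibits live vaccines on study, so a forward 6-month live-vaccine group would be nearly empty. Read backward, the flag is a legitimate baseline covariate. A forward reading remains possible for the 3-month flag, because non-live vaccines are not prohibited and Protocol 5.5.6 has on-trial vaccinations recorded.

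A reader might also extend the point to hsCRP response, since Protocol 9.4.4 says "the post-baseline subgroups of response in hsCRP response and target hsCRP levels achieved will be explored". Neither that section nor SAP 6.3.1 gives a model, clock or visit for it, and parts of the SAP's efficacy section are redacted. There is no specified analysis there to fault.

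**Conclusion.** The point holds for the early-drop models in SAP 7.4.5. As written, they relate infections to a blood count taken later. The size is modest: a true hazard ratio of 1.5 is reported as about 1.46-1.48, and a true hazard ratio of 1 as 0.97-1.05 at Visit 3 or 0.95-1.12 at Visit 4. The latter ranges need infection to halve or double the chance of a recorded drop. The direction cannot be known in advance, so it would be wrong to say that the plan simply overstates the risk from neutropenia. The rates, follow-up and effects on the count are assumed, and the finding depends on the SAP not specifying the clock elsewhere. No alpha-controlled test or randomized comparison between arms is affected. The SAP should be amended because the better method is cheap. For vaccination, only the direction of the window is unclear.

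**What to change.** In SAP 7.4.5, for each visit's model, start follow-up at that visit's sample date and include only patients who have a sample and no earlier infection. Alternatively, enter the drop as a time-dependent covariate from the sample date. Report how many patients are left out for want of a sample or because of an earlier infection. Describe the drop-by-treatment interaction as a non-randomized, exploratory comparison, because the drop arises after randomization. The baseline-neutropenia model needs no change.

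In SAP 7.4.1, state whether the vaccination windows run before or after baseline. If after, code vaccination as time-dependent from its date.

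The cost is a few sentences in the SAP and minor programming. With a landmark, the roughly 3-14% of first infections before the sample (assumed rates, days 46 and 91) leave these models; they stay in all the other infection analyses.

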**Table 7-8 NIH CTC version 4.0 grades for neutrophils**

CTC terms	Grade 1	Grade 2	Grade 3	Grade 4
Neutrophil count	<LLN - 1500/mm  ;	<1500 - 1000/mm  ;	<1000 - 500/mm  ;	<500/mm  ; <0.5 x

CTC terms	Grade 1	Grade 2	Grade 3	Grade 4
decreased	<LLN - $1.5 \times 10^9/L$	<1.5 - $1.0 \times 10^9/L$	<1.0 - $0.5 \times 10^9/L$	$10^9/L$

Whether neutrophil differences change over time will be assessed graphically, as well as using a repeated measures analysis of the continuous neutrophil count change from baseline with the covariates: treatment, time, time by treatment interaction, time since index MI, randomization plan, and baseline neutrophil count. Whether the occurrence of abnormalities (especially CTC grade  $\geq 3$ ) depends on the potential risk factor baseline neutrophil counts will be investigated using a cox regression model with time to first occurrence of abnormalities (CTC grade  $\geq 3$ ) with treatment, baseline neutrophil counts and treatment by baseline neutrophil counts interaction.

The number of patients that discontinued treatment and then returned to normal values or did not return to normal values, as well as those that did not discontinue and then returned to normal values or did not return to normal values will be summarized. The usage of concomitant medications given to normalize white blood cells counts/neutrophil counts will be summarized.

#### 7.4.7 Disorders of lipoprotein metabolism

Drug effects on lipids will be assessed by the laboratory analyses described in [section 7.3.2](#). Additional subgroups based on the use of lipid-lowering medications (including classes of these such as statins and fibrates) at baseline will be investigated. CV outcomes are the primary endpoint of this study and sub-group analyses for CV outcomes by baseline lipid values are planned (see [section 2.2](#)). Additionally, the dose of statins used will be tracked as described in [section 5](#). The incidence of adverse events such as myopathy that could result from different statin usage patterns may be explored based on the findings. The number of patients with persistently elevated triglycerides (>50% of visits with TG > 500 mg/dL), as well as the occurrence of adverse events such as pancreatitis (acute pancreatitis SMQ) that could result from persistent elevations will be summarized.

#### **7.4.8 Hypoglycemia**

As per the draft FDA requirements for the evaluation of prevention of diabetes, rates of hypoglycemia will be compared statistically between groups. Hypoglycemic events will be identified using the the SMQ Hypoglycaemia. Comparisons between treatment groups will be both done as time to first event analyses (including reporting the number of affected patients), as well as analyzing count data (number of patients with a certain number of hypoglycemic episodes – i.e. none, 1 episode, 2 episodes etc.) using negative binomial regression as described in [section 7.2](#). Baseline glucose and HbA1c values will be used as covariates in analyses.

Such reporting will be done for all hypoglycemic events as well as for events classified as severe by the investigator and events classified by the investigator as SAEs.

#### **7.4.9 Autoimmunity**

Autoimmunity reactions will be described including severity and seriousness, as well as occurrence at ANA antibodies by the end of the study.

#### **7.4.10 Injection site reactions**

Events of injection site reactions including including SAEs and those reactions leading to drug discontinuation will be summarized by treatment group and presenting both the frequency and the severity of the events.

